- Imminent preterm delivery due to maternal disease or fetal conditions
- Is not willing to wear CGM

Demographic information collected:

- Maternal age at enrollment (years)
- Gestational age at diagnosis of GDM (weeks)
- Gestational age at study inclusion (weeks)
- Gravidity and parity (G_P_ _ _ _)
- Race or ethnic group (self reported, Black, White, Asian, Hispanic, Other)
- Smoking status (current use in pregnancy at time of enrollment, yes/no)
- Alcohol use (current use in pregnancy at time of enrollment, yes/no)
- BMI at study entry (weight in kg / height in m²)
- History of GDM in a prior pregnancy (yes/no)
- Result of 50g OGTT (mg/dL)
- Results of 3hr 100 g OGTT (mg/dL)
- A1C at time of enrollment
- Other comorbidities including but not limited to: hypertension, autoimmune disease, thyroid dysfunction, polycystic ovarian syndrome, cardiac disease, pulmonary disorders, thromboembolic disorders

Vulnerable populations:

- We will not involve vulnerable populations such as those < 18 years old, prisoners, or mentally impaired in this study.

Study design

- Hypothesis:
 - The increased data and feedback provided by real-time CGM will improve glycemic control in gestational diabetic patients over routine SMBG.
- Primary Outcome:
 - Mean blood glucose (mg/dL) in the real-time CGM group compared to SMBG group during the 4th week of study from data collected on the 6 day of CGM use during that week.
- Covariates
- Glycemic outcomes:
 - Between Groups -Failed dietary therapy (started on medication), time spent in normoglycemia week 1 vs. week 4 (min/day), time spent in hyperglycemia week 1 vs. week 4 (min/day), time spent in hypoglycemia week 1 vs. week 4 (min/day)
 - Within Groups - Time spent in normoglycemia week 1 vs. week 4 (min/day), time spent in hyperglycemia week 1 vs. week 4 (min/day), time spent in hypoglycemia week 1 vs. week 4 (min/day)
- Maternal outcomes :

- BMI at time of delivery (kg/m^2)
- Gestational hypertension (defined as SBP ≥ 140 mm Hg or DBP ≥ 90 mmHg, on 2 occasions at least 4 hrs apart)
- Preeclampsia (defined as gestational hypertension plus either new-onset proteinuria (≥ 300 mg/24 2hrs, protein:creatinine ≥ 0.3 mg/dL), thrombocytopenia (platelet count $< 100,000/\mu\text{L}$), elevated AST or ALT ($> 2x$ upper limit of normal), renal insufficiency (serum creatinine > 1.1 mg/dL or an unexplained doubling of creatinine), pulmonary edema, or cerebral or visual symptoms)
- HbA1C values week 1 compared to week 4 (%)

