not needed. Only after a participant has been enrolled into the study will an envelope be opened and the patient allocated to a group.

Procedures

- Procedures
- [name] will review charts of new Gestational Diabetes patients whom are scheduled to attend the gestational diabetes classes at Eastern Virginia Medical School (Mondays) and EVMS Sentara Princess Anne MFM Clinic (Fridays). He will select those patients who meet the study criteria based on the inclusion/exclusion of the study. He will then give that information to Research Coordinator, [name]. [name] will call patients a day before their scheduled Diabetes class to discuss this study. If patient agrees to participate, [name] will meet them right before class to enroll (review and sign consent forms). [name] will do the same for Sentara Princess Anne patients.
- Patients will be randomized to two arms: Traditional Management (20 patients); using the Ipro2 CGM and CGM management (20 patients); using the “real time” CGM. [name] will randomize patients in arms according to names drawn from an envelope during the time of consent. Research activities will occur at standard of care clinical visits. Patients are required to attend research study visits every 7 days for 4 weeks.
- During each visit data such as demographic data, glycemic levels, primary and secondary maternal and neonatal outcomes will be collected. At each visit CGM will be downloaded, a new sensor will be placed for the next 7 days, clinicians will manage GDM per EVMS GDM protocols, and DM will provide dietary reviews/education. [name] will download CGM, add interval data points to database and replace CGM for EVMS patients. [name] will do the same for EVMS Sentara (Princess Anne) patients. Data will be printed and transferred to data collection sheets. All data from the forms will be uploaded into a de-identified electronic database (Redcap, EVMS, set up by EVMS CHAD). All forms will be placed in the patient’s research folder.
- Patients charts will be kept locked in a file cabinet in the research coordinator’s office. Only members of the study will have access to this file cabinet.
- Outcome data will be collected at the completion of study. The data from the CGM reports will not be shared with the clinical provider during the clinic visits.

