- Both [name] and [name] will receive training on both devices from a local Medtronic representative. They will then educate the patients on the proper use and function of these devices at the time of enrollment.
- Both CGM devices are FDA approved and produced by Medtronic. Each measures 288 glycemic values/day. The ipro2 blindly collects values w/o a screen so the patient is not aware of the data. The 530g CGM has a screen that displays the values that the patient can see. Both groups will also perform SMBG. SMBG is used to calibrate the CGM and for the clinician’s review to make clinical decisions.
- [name] and [name] will be each other’s backups.
- Group 1: real-time CGM for 4 weeks with weekly clinic visits
- Group 2: blinded CGM for 4 weeks with weekly clinic visits
- If possible, provide a step-by-step account of each stage of your study. See attached PDF flow sheet
- Demographic data will be collected on forms at study inclusion. Outcome data will be collected on forms at study completion. Weekly CGM data will be downloaded by a study investigator and the data will be printed and transferred to forms. All forms will be placed in the patient’s research folder. All data from the forms will be uploaded into a de-identified electronic database (Redcap, EVMS, set up by EVMS CHAD).
- We will be collecting the demographic, primary outcome, maternal/neonatal/glycemic secondary outcome data as outlined above
- All study investigators and the research coordinators will have access to the research folders that include identifying information on study subjects. These folders will be kept in

a locked file cabinet in the locked office of the research coordinator. No one else will have access to this data.

Risk

- There are very few known risk to patients involved in this study, beyond what we would normally expect from any pregnancy with gestational diabetes. Risks and side effects related to continuous glucose monitors (CGM) include skin irritation at the sensor site, infection at the sensor site and pain at the sensor site.
- Study team will inform each patient enrolled on this study of these risks during the review of the informed consent. Research team will ensure patient has access to the investigator and research coordinator's telephone number in the case of a side effect.
- If the patient experiences any issues with wearing the CGM device, it will be removed and she will not be required to wear another device (page 9 of application).

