- There is a risk associated with allowing your data to be saved is the release of personal information from your study record. Research team members will strive to protect patient records such as name, address, social security number, phone number and will notify patient if information is breached.

Statistical Analysis Plan

- Sample Size Calculations:
 - Estimated mean blood glucose of a pregnant women with GDM using CGM: 102.6 mg/dL +/- SD 9 mg/dL²⁴
 - Randomized trial, 1:1 allocation, continuous variable outcome
 - Alpha = 0.05
 - Beta = 0.80
 - 10 patients/arm to detect a 20% decrease in mean blood glucose
 - Goal: 20 patients/arm with interim analysis after 10 patients/arm have completed the trial
- Other analysis will be with the guidance and aide of EVMS CHAD:
 - All data will be analyzed with intention to treat. Normality of data will be tested for all continuous variables using the Kolmogorov–Smirnov test. Normally distributed parameters will be presented as mean±SD, and non-normally distributed values are presented as median (range). Categorical data will be reported as frequency and percentage. Parametric (the Student's t-test) or nonparametric (the Mann–Whitney U-test) comparisons will be used based on the distribution of variables. The pre/post change in blood glucose between the two arms will be compared using regression models, when treatment group will be treated as a qualitative independent variable. To assess the significant difference between the two arms adjusting for covariates, ANCOVA model will be used.. A p < 0.05 will be accepted as statistically significant. SAS 9.4 (SAS Institute Inc, Cary, NC) will be used for statistical analysis.

REFERENCES:

1. Bulletins--Obstetrics CoP. Practice Bulletin No. 137: Gestational diabetes mellitus. *Obstet Gynecol*. 2013;122(2 Pt 1):406-416.
2. Moyer VA, Force USPST. Screening for gestational diabetes mellitus: U.S. Preventive Services Task Force recommendation statement. *Ann Intern Med*. 2014;160(6):414-420.
4. Wier LM WE, Burgess J, Elixhauser A. Hospitalizations related to diabetes in pregnancy. In.

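### The between-arm pre/post change in glucose has no like-for-like pre-treatment value on the text shown; measured from week 1, it subtracts any effect the display has already had

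*Protocol*

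**What the plan says.** All references are to the protocol.

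- **Analysis.** The Statistical Analysis Plan section states: "The pre/post change in blood glucose between the two arms will be compared using regression models". It adds: "To assess the significant difference between the two arms adjusting for covariates, ANCOVA model will be used". It neither says which measurement is the pre value nor lists the covariates.
- **Secondary glycemic outcomes.** Under Study design, the between-arm line reads "Between Groups -Failed dietary therapy (started on medication), time spent in normoglycemia week 1 vs. week 4 (min/day", and continues in the same form for hyper- and hypoglycemia. A separate line reads "Within Groups - Time spent in normoglycemia week 1 vs. week 4 (min/day". Under maternal outcomes there is also "HbA1C values week 1 compared to week 4".
- **Primary outcome.** Mean glucose in week 4, compared between the arms. Week 1 plays no part in it.
- **Timing.** Under Procedures, the coordinator "will randomize patients in arms according to names drawn from an envelope during the time of consent". On device training: "They will then educate the patients on the proper use and function of these devices at the time of enrollment". Group 1 has real-time CGM, with a screen the patient can see, for 4 weeks; Group 2 has blinded CGM for the same 4 weeks. On the weekly visits: "At each visit CGM will be downloaded, a new sensor will be placed for the next 7 days".
- **Values before the device starts.** The demographic list includes the 50 g and 100 g glucose test results and A1C at enrolment. No run-in and no pre-randomisation CGM or self-monitored glucose is described. The flow sheet is referred to but not shown.

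**The concern.** A pre/post comparison between randomised arms is meant to start from a value that treatment cannot have touched. Here the first CGM week follows randomisation and device training, and the real-time arm can already see its readings. The trial's rationale is constant feedback, so some effect within the first 7 days is plausible, though nothing in the protocol gives its size.

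If week 1 serves as the pre value, whatever the display achieves in that week is treated as baseline and removed, wholly (change score) or in part (ANCOVA). A secondary analysis could then show a much smaller effect than the week-4 primary analysis, or none, and appear to contradict it.

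**Working it through.** **Inputs from the protocol (sample size paragraph).** Mean 102.6 mg/dL, SD 9, a 20% decrease, alpha 0.05, 20 per arm. The planned effect is D = 0.20 × 102.6 = 20.52 mg/dL.

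**Assumptions, not in the protocol.** A two-sided test; SD 9 in each week; f, the share of D already present in week 1; rho, the week 1 to week 4 correlation, taken as 0.3, 0.5 and 0.7.

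**The plan's own figure.** The protocol states 10 per arm for the primary outcome (its 0.80 is labelled beta but read here as power). A t-test on its inputs reaches 80% with 5 per arm (power 0.77 at 4, 0.88 at 5, above 0.99 at 10), so the stated 10 is not reproduced. That is a separate matter and is no evidence on this point. The protocol gives no figure for the secondary comparisons.

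**Step 1: is week 1 on treatment?** Randomisation takes place at consent, training at enrolment, and the display runs for all 4 weeks. Yes, on the text shown.

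**Step 2: what could the pre value be?** OGTT and A1C precede the device but are different measures from CGM mean glucose. For CGM glucose, week 1 is the only like-for-like candidate.

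**Step 3: what is then estimated?** The arms differ by fD in week 1 and by D in week 4.

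- Change score: D - fD = (1-f)D, with SD 9 × sqrt(2(1-rho)) = 10.65, 9.00 and 6.97 for rho 0.3, 0.5 and 0.7.
- ANCOVA with week 1 as covariate: D - rho × fD = (1 - rho × f)D.

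**Step 4: results at D = 20.52.** Change-score power is from the noncentral t distribution with 38 df, ANCOVA power from simulation with 37 df. Entries separated by slashes are for rho 0.3/0.5/0.7.

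| f | Change score, mg/dL | Power | ANCOVA on week 1, mg/dL | Power |
|---|---|---|---|---|
| 0.5 | 10.3 | 0.84/0.94/0.995 | 17.4/15.4/13.3 | above 0.99 |
| 0.75 | 5.1 | 0.32/0.42/0.62 | 15.9/12.8/9.7 | 0.98/0.96/0.93 |
| 1 | 0 | 0.05 | 14.4/10.3/6.2 | 0.90/0.74/0.48 |

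The plain week-4 comparison estimates 20.5 with power above 0.99 in every row.

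**Step 5: a smaller effect.** Suppose the true effect is half the planned one, D = 10.26 (assumption), and f = 0.5.

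- Change score: 5.1 mg/dL, power 0.32/0.42/0.62.
- ANCOVA on week 1: 8.7/7.7/6.7 mg/dL, power 0.84/0.82/0.86.
- Week-4 comparison: 10.3 mg/dL, power 0.94.

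**Step 6: an effect in week 1 only.** If the arms differ by 10.26 in week 1 and by nothing in week 4, the change score estimates -10.26. ANCOVA on week 1 estimates -rho × 10.26, which is -5.1 at rho 0.5, and rejects in about 41% of simulated trials. This is a spurious difference in the opposite direction.

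**Time in range.** The protocol gives no SD for it, and f may differ from that for mean glucose, so no figure is computed.

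**The case against.** The strongest reply is that the protocol never names week 1 as the pre value or as a covariate, and that defining baseline and listing covariates is commonly left to a statistical analysis plan, which may exist but is not shown. The covariate list can indeed wait. The pre/post comparison cannot be rescued in that way: the protocol commits to it, and on the text shown no like-for-like pre-device value exists for a later document to point to. The missing flow sheet could change this only if it shows such a measurement.

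A second reply concerns time in range. The protocol has a separate within-group line for change over time, so the between-group line may mean comparing the arms at week 1 and again at week 4. That reading is open and has no bias. A reader might infer that the time-in-range outcomes are certainly attenuated; the text does not support that.

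A third reply is that a difference in week 1 to week 4 change is a legitimate measure of how the arms diverge during treatment. So it is, if labelled that way; it is not a pre/post effect of the device.

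It is also fair that f and rho are assumptions, and that at the planned effect with f = 0.5 the change score still has power of 0.84 or more. There the harm is a shrunken estimate. HbA1C may be exempt, since its week-1 value may be the A1C taken at enrolment.

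**Conclusion.** The point stands as a minor one on secondary analyses. The between-arm pre/post change in glucose can be carried out like for like only from an on-treatment week, and it then estimates (1-f)D, or (1-rho*f)D by ANCOVA. At f = 0.5 and rho = 0.5 the planned 20.5 mg/dL becomes 10.3 or 15.4. At the planned effect, serious loss of power needs f of about 0.75 or more for the change score, or near 1 for ANCOVA. At half that effect, change-score power is already 0.32 to 0.62 at f = 0.5, against 0.94 for a plain week-4 comparison.

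This rests on the text shown, on SD 9 in both weeks, and on assumed f and rho. If there is no effect in week 1, there is no bias.

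Two stronger readings are tempting and do not hold. One is that the primary result is biased: as defined it does not use week 1, and it would be affected only if the ANCOVA were applied to it with week 1 as covariate. The other is that the error can only shrink the effect or vanish when week 4 shows none: that fails if an effect exists in week 1 alone.

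**What to change.** In the glycemic outcomes list and in the Statistical Analysis Plan section, state the following:

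- The between-arm comparisons of mean glucose and of time in normo-, hyper- and hypoglycemia are made at week 4.
- The regression or ANCOVA takes the week-4 value as outcome and adjusts only for values collected before the device starts (enrolment A1C, OGTT results), not for week-1 CGM.
- Week 1, and the week 1 to week 4 change, are reported as descriptive on-treatment results. The within-group lines can stay under that label.

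**Cost.** No new data or visits are needed, but one stated secondary analysis is replaced rather than merely clarified. Some precision is given up if week 1 carries little of the effect and rho is high. At D = 10.3 and rho 0.7, power is 0.94 without week 1 as covariate, against 0.998 with it at f = 0 and 0.976 at f = 0.25. At rho 0.5 the gain from including it is gone by f = 0.25 (0.93 or 0.94 either way). OGTT and A1C may correlate only weakly with week-4 CGM glucose, so adjusting for them may recover little of that precision. A CGM change from a true baseline remains unavailable, because no pre-randomisation CGM is described.

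### Maternal hypoglycemia is compared only for weeks 1 and 4, so half of the CGM time the trial already downloads falls outside its only maternal hypoglycemia outcome

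*Protocol*

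**What the plan says.** The glycemic outcomes in the protocol's Study design section include "time spent in hypoglycemia week 1 vs. week 4 (min/day", once between groups and once within groups. Normoglycemia and hyperglycemia have the same two weeks. The primary outcome uses week 4 only.

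The Procedures describe a longer exposure, equal in the two arms: "Group 1: real-time CGM for 4 weeks with weekly clinic visits" and "Group 2: blinded CGM for 4 weeks with weekly clinic visits". Visits are weekly: "Patients are required to attend research study visits every 7 days for 4 weeks". Every week's trace is captured: "At each visit CGM will be downloaded, a new sensor will be placed for the next 7 days", and "Weekly CGM data will be downloaded by a study investigator and the data will be printed and transferred to forms". The forms are then entered in the study database. On recording density, the Procedures say of the two devices: "Each measures 288 glycemic values/day".

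No other maternal hypoglycemia measure is listed. The hypoglycemia item among the neonatal outcomes concerns the infant. The Risk section opens its list with "Risks and side effects related to continuous glucose monitors (CGM) include skin irritation at the sensor site" and goes on to infection and pain at the same site; it does not name maternal hypoglycemia.

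**The concern.** A comparison of the first and last week is a natural way to show a trend in glycemic control. It suits an unwanted effect less well, because such an effect counts whenever it occurs during exposure. The trial aims to lower glucose: its sample size section takes a mean of 102.6 mg/dL and a 20% decrease, that is 102.6 × 0.80 = 82.1 mg/dL. More time at low values is an obvious thing to look for alongside that aim.

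The stated window could miss it in three ways.

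- **Lows confined to weeks 2 and 3 are not counted.** Women are managed weekly and starting medication is itself a listed outcome, so treatment can change during those weeks.
- **Early removal leaves no week 4 value.** The Risk section allows the device to be taken off for good if a woman has trouble wearing it. If that happens in week 3, what was recorded in weeks 2 and 3 has no place in the outcome.
- **Week 1 is not a baseline.** Women are taught to use the device at enrollment, each arm is assigned its own device for all 4 weeks, and no run-in is described. Week 1 is already a week of real-time display in one arm and of blinded recording in the other.

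At stake is a report of no difference in hypoglycemia while the trial's own database holds an excess that the listed comparison could not show.

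**Working it through.** The protocol gives no figure for time in hypoglycemia (no expected value, SD or between-week correlation), so there is none to reproduce. The sample size calculation concerns mean glucose and is not an input here.

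**1. Share of exposure covered.** Inputs from the Procedures: 4 weeks of CGM, 7 days each, 288 readings a day. From the Statistical Analysis Plan section: 20 women per arm, 40 in all.

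| | Weeks 1-4 | Weeks 1 and 4 |
|---|---|---|
| Days per woman | 4 × 7 = 28 | 2 × 7 = 14 |
| Readings per woman | 28 × 288 = 8,064 | 14 × 288 = 4,032 |
| Woman-days, 40 women | 40 × 28 = 1,120 | 40 × 14 = 560 |

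The comparison covers 14/28 = 50% of planned CGM time. These are planned maxima. If only 6 days a week were used, as one may read the primary outcome, the share would be 12/24, again half.

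**2. What a change score does with a sustained excess.** Let the control arm's mean be c₁ in week 1 and c₄ in week 4, and let the real-time arm have e more minutes per day in every week. Then

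- change, control arm: c₄ − c₁
- change, real-time arm: (c₄ + e) − (c₁ + e) = c₄ − c₁
- difference in change: 0, whatever the size of e
- difference in the mean over weeks 1-4: (e + e + e + e)/4 = e

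If the excess m occurs only in weeks 2 and 3, weeks 1 and 4 differ by 0 under any reading, and the 4-week mean differs by (0 + m + m + 0)/4 = m/2.

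**3. Precision.** Assume equal variance σ² in each week and an equal correlation ρ between any two weeks. The mean of k weeks then has variance σ²[1 + (k − 1)ρ]/k.

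- 4 weeks: σ²(1 + 3ρ)/4
- weeks 1 and 4: σ²(1 + ρ)/2
- ratio of standard errors: √{[(1 + 3ρ)/4] / [(1 + ρ)/2]}

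| ρ (assumed) | Variance, 4 weeks (× σ²) | Variance, weeks 1 and 4 (× σ²) | SE lower by |
|---|---|---|---|
| 0 | 0.250 | 0.500 | 29% |
| 0.3 | 0.475 | 0.650 | 14.5% |
| 0.5 | 0.625 | 0.750 | 8.7% |
| 0.7 | 0.775 | 0.850 | 4.5% |
| 0.9 | 0.925 | 0.950 | 1.3% |

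The reference in this table is a mean of weeks 1 and 4. The protocol sets those weeks against each other and does not average them, so the table shows only what two further weeks add to an average level.

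**The case against.** The best case for the protocol is that this is a coherent choice. One pair of weeks serves all three time-in-range outcomes and the HbA1c comparison. Nothing calls time in hypoglycemia a safety endpoint, and an unseen SAP could add a table over all weeks. The data are stored in any case. All of this is true, so the point is a weak outcome definition and neither a contradiction nor an arithmetic error. It still stands, because the protocol itself fixes the window for the only maternal hypoglycemia outcome it lists.

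A second objection is that the display may have little direct route to lows. The pump is inactivated and gives no insulin, treating clinicians do not see the CGM reports at visits, and clinical decisions rest on SMBG in both arms. Any difference between arms would have to come mainly through the woman's own behavior. That lowers the prior concern but does not justify leaving out half of the record.

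Several stronger readings are tempting, and the document does not support them.

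- **That hypoglycemia is the trial's main harm.** That is a judgement; the Risk section names only sensor-site effects.
- **That a woman with lows in weeks 2 and 3 contributes nothing.** She contributes her week 1 and week 4 minutes; only the lows in between go uncounted.
- **That half the exposure is half the information.** Weeks within a woman are correlated, and the precision gain shrinks as the correlation rises.
- **That the bound on a zero event rate would be halved.** With 40 or 80 woman-weeks per arm, the one-sided 95% limits are 1 − 0.05^(1/40) = 7.2% and 1 − 0.05^(1/80) = 3.7%. These treat weeks as independent and need a yes/no event, which the protocol does not define. With fully correlated weeks, both windows reduce to 20 women and 1 − 0.05^(1/20) = 13.9%, with no gain.

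**Conclusion.** The concern holds as a minor point of outcome definition. Half of the planned CGM time, 14 of 28 days per woman, is outside the protocol's only maternal hypoglycemia outcome although it is downloaded and stored. The share follows from the protocol's own schedule without further assumption.

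The argument about a hidden sustained excess is conditional. It applies if week 1 versus week 4 is analysed as a change. The Statistical Analysis Plan section plans a pre/post comparison between arms for blood glucose, which makes that reading plausible, but it does not say so for hypoglycemia. If the arms are instead compared separately in each of the two weeks, a sustained excess can be seen, and only lows in weeks 2 and 3 and the missing week 4 values remain at issue.

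The precision figures rest on an assumed equal correlation and equal variance across weeks, and the gain may be as small as about 1%. The case therefore rests on coverage of the exposure.

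A reader might infer that the primary outcome is compromised or that safety data will be lost. Neither follows: the primary outcome is mean glucose in week 4 and is untouched, and the traces for weeks 2 and 3 remain available. What is missing is a prespecified comparison that uses them.

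**What to change.** Add one item to the between-group glycemic outcomes: time in hypoglycemia (min/day) over all recorded CGM time in weeks 1-4, compared by arm. Include every woman with any trace, up to sensor removal, and report the recorded days per arm beside it so that unequal follow-up is visible. Apply the same maternal hypoglycemia cut-off that the trial uses for its week 1 and week 4 outcome, and keep those outcomes as listed.

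Add a count of women with any hypoglycemic episode only if the protocol or SAP states an episode definition. The one numerical hypoglycemia cut-off printed in the protocol, below 35 mg/dL, is for neonates and does not serve this purpose.

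The cost is a line of text and one more secondary analysis, to be read with the usual caution about several secondary comparisons at p < 0.05. It needs no new data, visits or patients and changes no clinical management.

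### Week 1 vs week 4 changes in time in range are listed as within-group outcomes with no descriptive label, and week 1 is already on the allocated device, so they cannot support a claim for real-time CGM

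*Protocol*

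**What the plan says.** The hypothesis in the protocol's Study design section is comparative: real-time CGM should improve control relative to routine SMBG. The primary outcome is comparative too: "Mean blood glucose (mg/dL) in the real-time CGM group compared to SMBG group during the 4th week of study".

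The glycemic outcomes follow in two bullets. The first reads "Between Groups -Failed dietary therapy (started on medication), time spent in normoglycemia week 1 vs. week 4 (min/day" and goes on to hyper- and hypoglycemia. The second repeats the three measures inside each arm: "Within Groups - Time spent in normoglycemia week 1 vs. week 4 (min/day", again followed by hyper- and hypoglycemia. Neither bullet is marked descriptive or exploratory.

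The Statistical Analysis Plan section names Student's t-test and the Mann–Whitney U-test and adds two between-arm models: "The pre/post change in blood glucose between the two arms will be compared using regression models", and "To assess the significant difference between the two arms adjusting for covariates, ANCOVA model will be used". It names no paired test. It closes with one threshold for everything: "A p < 0.05 will be accepted as statistically significant".

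Under Procedures, patients in both arms attend every 7 days for 4 weeks. At each visit clinicians manage the diabetes under the local protocol and "DM will provide dietary reviews/education". Both arms also perform SMBG. Allocation takes place at consent, and each group then wears its allocated device for 4 weeks.

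**The concern.** Two separate problems arise.

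First, a change inside one arm does not use the randomised comparison. Both arms receive education, SMBG and medication where needed, so both may improve, or drift with advancing gestation, whatever the device. A significant change in the real-time arm beside a non-significant one in the blinded arm looks like a device effect, but it is not evidence that the arms differ. Listing these changes as outcomes under a general p < 0.05 rule leaves room for that reading.

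Second, week 1 is not a baseline. Patients in the real-time arm already see their values during it. A week 1 to week 4 change therefore removes whatever the display achieved in the first week. This affects the between-group version of the outcome as well as the within-group one.

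At stake is what the time-in-range results can support. These are secondary outcomes.

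**Working it through.** **The plan's own figure.** There is none on this point. The sample-size figures concern mean glucose and give no expected change, or SD of change, for time in range. Only the arm size and the threshold are used here.

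**Inputs**
- Arm size: 20 per arm (Statistical Analysis Plan, goal).
- Threshold: 0.05 (same section). Sidedness is not stated, so two-sided is assumed.
- Measures: three (normo-, hyper-, hypoglycemia) in two arms, giving 3 × 2 = 6 within-arm comparisons (Study design).
- Assumption: the true mean change is d standard deviations of the within-patient change, equal in both arms. The documents give no value, so d runs from 0 to 1.0.
- Assumption: a paired t-test within each arm, since no within-arm test is named.

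**Step 1: one-arm-only significance when the arms do not differ.** Let p be the power of the paired test in one arm, from the noncentral t distribution with 19 degrees of freedom and noncentrality d × √20. The arms are independent, so:
- P(exactly one arm significant) = 2p(1 − p)
- P(only the real-time arm significant) = p(1 − p)

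For example, at d = 0.3, p = 0.247 and 2 × 0.247 × 0.753 = 0.372.

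| Common change d | p | Exactly one arm | Real-time arm only |
|---|---|---|---|
| 0 | 0.050 | 9.5% | 4.8% |
| 0.2 | 0.136 | 23.5% | 11.7% |
| 0.3 | 0.247 | 37.2% | 18.6% |
| 0.46 | 0.497 | 50.0% | 25.0% |
| 0.66 | 0.799 | 32.1% | 16.0% |
| 0.8 | 0.924 | 14.1% | 7.0% |
| 1.0 | 0.989 | 2.3% | 1.1% |

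(Percentages come from unrounded p.) At 10 per arm, the planned interim size, the pattern shifts to larger changes: 9.5% at d = 0, 49.7% at d = 0.66 and 31.6% at d = 1.0.

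**Step 2: check by simulation.** With 100,000 simulated trials of 20 per arm at d = 0, 0.3, 0.46 and 0.66, exactly one arm was significant in 9.7%, 37.3%, 50.0% and 32.0%. The between-arm t-test on change was significant in 5.0%, 5.0%, 5.0% and 5.1%.

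**Step 3: do not multiply over the three measures.** The figures are per measure. The three times come from the same day, so more of one means less of the others. They are not independent, and a combined figure that treats them as independent would mislead.

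**Step 4: what a week 1 to week 4 change estimates.** Let E1 and E4 be the device effects (difference between arms) in weeks 1 and 4.
- Change inside the real-time arm: common change + (E4 − E1).
- Difference between arms in change: E4 − E1.
- Difference between arms at week 4: E4.

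If the display works at once and its effect holds, E1 = E4 and the between-arm difference in change is zero however large the benefit. Only the week-4 difference recovers E4. The primary outcome already has that form, but the time-in-range outcomes do not.

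**The case against.** The strongest reply is that the plan already contains the right comparison. The bullet just above the within-group one lists the same three measures between groups. The hypothesis and primary outcome are between-arm, and regression and ANCOVA between arms are planned. No within-arm test is specified, and the within-group results are openly labelled as such. A descriptive label could also be left to a separate statistical analysis plan.

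Much of this stands. A reader might infer that the investigators mean to conclude a device effect from within-arm p-values, or that the within-arm comparisons are the only analysis of time in range. The documents support neither. Within-arm testing itself is an inference from the outcome list and the general threshold.

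Two things remain. The pre/post regression is worded for blood glucose, not for the three times. And the between-group bullet uses the same week 1 to week 4 contrast, so Step 4 applies to it too. That contrast is fixed in the protocol's own outcome list.

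The size is also open to challenge, because p depends on a change that nobody has stated. Power values around one half give the largest figures, so the whole range has to be shown. The pattern that would favour the device is only half of the exactly-one-arm figure, and its like-for-like comparator is 2.5% (one tail of the between-arm test), not 5%.

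**Conclusion.** The point holds in a limited form. The within-group week 1 vs week 4 outcomes cannot bear on the hypothesis, and nothing marks them as descriptive. With 20 per arm and no true difference between arms, the chance per measure that exactly one arm reaches p < 0.05 runs from about 2% to 50%, depending on an assumed common change of 0 to 1.0 SD. For the real-time arm alone it is half of that, at most 25%. The between-arm test stays near 5%. These figures assume two-sided paired t-tests and independent arms.

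Separately, and without any such assumption about size, a week 1 to week 4 change leaves out an effect gained in week 1, within or between arms. This rests on allocation at consent and device use from the start. No run-in is described, but the flow sheet the protocol refers to was not available.

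A reader might infer a false-positive rate of up to 50% for the trial. That does not follow: the figure is the chance of a pattern that could be misread, in secondary outcomes, under one assumed change. The primary analysis is unaffected. This is a worthwhile improvement, not a serious flaw.

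**What to change.** 1. Mark the within-group results as descriptive: week-1 and week-4 values and the change by arm, each with an estimate and 95% CI and no p-value.
2. Replace the between-group week 1 vs week 4 contrast for the three times with the between-arm difference at week 4, adjusted for one pre-randomisation value already collected. An enrolment OGTT value would serve. Enrolment A1C is possible, but the Background section notes that it reads falsely low in pregnancy and cannot identify postprandial hyperglycemia. Inclusion requires abnormal OGTT values, which narrows their range and may limit the gain in precision. The change of contrast does not depend on which covariate is chosen.
3. State that any conclusion about real-time CGM on time in range rests on that week-4 difference.

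The cost is a few lines of text. No new data, no change in sample size and no change to the primary analysis are needed. The downside is that the trial could no longer report that a single arm improved significantly.
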